hypothyroidism (7.2%), pneumonitis (2.9%), hyperthyroidism (2.2%), colitis (1.3%) and skin AEOSI (1.3% including all terms). Based on the mechanism of action of MK-3475 and similar immunomodulatory agents, the Sponsor is interested in potential irAEs, and encourages appropriate investigation of signs and symptoms suggestive of these.

Consultation with the appropriate medical specialist should be considered when investigating a possible irAE. These events can occur after the first dose to several months after the last dose of treatment. Mild irAEs are usually treated symptomatically and do not require dosing delays or discontinuation. Higher grade and persistent lower grade irAEs typically necessitate withholding or discontinuing treatment and administration of systemic steroids or other immunosuppressive agents (such as tumor necrosis factor blockers), when systemic steroids are not effective. Early recognition of irAEs and initiation of treatment are critical to reduce the risk of complications, since the majority of irAEs are reversible with the use of steroids and other immune suppressants.

Identification and Treatment of irAEs

If an irAE is suspected, a thorough evaluation should be conducted in an effort to possibly rule out neoplastic, infectious, metabolic, toxin or other etiologic causes prior to diagnosing an irAE. Serological, immunological, and histological (biopsy) data should be considered to support the diagnosis of an immune-related toxicity.

A separate document entitled Pembrolizumab Program (MK-3475) Event of Clinical Interest Guidance Document is maintained and distributed to investigational sites along with this IB and study protocols. Please refer to this guidance document in conjunction with this IB when assessing irAEs. Updates and modifications to the irAE guidance document will be made and distributed to Investigators to provide the most current information, and therefore will be independent of the IB update cycle.

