Colitis (including microscopic colitis) occurred in 4 (1%) of 411 patients, including Grade 2 or 3 cases in 1 (0.2%) and 2 (0.5%) patients, respectively, receiving KEYTRUDA in Trial 1. The median time to onset of colitis was 6.5 months (range 2.3-9.8). The median duration was 2.6 months (range 0.6 weeks-3.6 months). All three patients with Grade 2 or 3 colitis were treated with high-dose corticosteroids (greater than or equal to 40 mg prednisone or equivalent per day) with a median initial dose of 70 mg/day of prednisone or equivalent; the median duration of initial treatment was 7 days (range 4-41), followed by a corticosteroid taper. One patient (0.2%) required permanent discontinuation of KEYTRUDA due to colitis. All four patients with colitis experienced complete resolution of the event. Monitor patients for signs and symptoms of colitis. Administer corticosteroids for Grade 2 or greater colitis. Withhold KEYTRUDA for moderate (Grade 2) or severe (Grade 3) colitis, and permanently discontinue KEYTRUDA for life-threatening (Grade 4) colitis.

Immune-Mediated Hepatitis

Hepatitis (including autoimmune hepatitis) occurred in 2 (0.5%) of 411 patients, including a Grade 4 case in 1 (0.2%) patient, receiving KEYTRUDA in Trial 1. The time to onset was 22 days for the case of Grade 4 hepatitis which lasted 1.1 months. The patient with Grade 4 hepatitis permanently discontinued KEYTRUDA and was treated with high-dose (greater than or equal to 40 mg prednisone or equivalent per day) systemic corticosteroids followed by a corticosteroid taper. Both patients with hepatitis experienced complete resolution of the event.

Elevated transaminases and alkaline phosphatase may be seen during treatment. Treatment should be interrupted when transaminase or alkaline phosphatase increases are accompanied by Grade 3 total bilirubin, and/or Grade 3 coagulation tests (e.g., International Normalized Ratio [INR]), or if subjects are clinically symptomatic.

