Evaluation of subjects with elevated transaminases, bilirubins, and alkaline phosphatase should involve a workup to assess for infection (SBP or other), viral reactivation (if relevant), vascular thrombosis, biliary obstruction, possible hepatotoxic medications, tumor progression, alcohol toxicity, and effects of pembrolizumab. At baseline, all subjects should be assessed for HBsAg, HBsAb, anti-HBc antibody, HBeAg, and anti-HCV. As described above, a viral load <100 IU/mL is required for study entry, and with active HBV must have also been treated with antiviral therapy for ≥ 3 months before initiation of study treatment. Subjects with controlled HBV on therapy should stay on this same therapy throughout pembrolizumab treatment. Subjects who are positive for HBsAg or anti-HBc (but negative for HBsAg and HBV DNA), should be assessed for HBV viral load, HBsAg, HBsAb, anti-HBc antibody, HBeAg every 3 weeks, independent of treatment delays.

Subjects with chronic infection by hepatitis C virus (HCV) with successful treatment (defined as SVR12 or SVR24) may be included. HCV genotype should also be recorded at baseline. **Untreated HCV positive subjects are eligible, and if stable after 6 months on pembrolizumab, additional antiviral treatment for HCV may be considered per local standard of care.** Viral loads should be assessed for those with an underlying viral etiology q 3 weeks. They should also be checked if there is an elevation in ALT $> 3 \times$ baseline, a tenfold or greater increase in HBV or HCV DNA $>$ baseline, or an absolute increase in HBV or HCV DNA $> 10^5$ c/mL. If evidence of reactivation is present, the Sponsor should be consulted within 24 hours, and pembrolizumab treatment should be interrupted. A hepatology consult should be obtained.

- For **Grade 2** AST/ALT or alkaline phosphatase events (if normal or Grade 1 at baseline) and no other etiology is found, monitor liver function tests weekly.

- For **Grade 3-4** AST/ALT, alkaline phosphatase events if normal at baseline), or $>3\times$ baseline (if greater than $2\times$ ULN at baseline) and no other underlying etiology is found, consider treatment with intravenous corticosteroids for 24–48 hours. When improved to baseline (for those with levels $\geq 2\times$ ULN at baseline) or Grade 1 or less (for those with normal baseline values), a steroid taper should be started and continued over no less than 4 weeks.

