- For **Grade 2-3** total bilirubin or PT/INR, pembrolizumab should be interrupted and steroids given as above. If values don't improve within 12 weeks from date of diagnosis of grade 3 toxicity to baseline or Grade 0-1, pembrolizumab should be permanently discontinued.
- For **Grade 4** total bilirubin or PT/INR, pembrolizumab should be permanently discontinued.

Immune-Mediated Hypophysitis

Hypophysitis occurred in 2 (0.5%) of 411 patients, consisting of one Grade 2 and one Grade 4 case (0.2% each), in patients receiving KEYTRUDA in Trial 1. The time to onset was 1.7 months for the patient with Grade 4 hypophysitis and 1.3 months for the patient with Grade 2 hypophysitis. Both patients were treated with high-dose (greater than or equal to 40 mg prednisone or equivalent per day) corticosteroids followed by a corticosteroid taper and remained on a physiologic replacement dose. Monitor for signs and symptoms of hypophysitis. Administer corticosteroids for Grade 2 or greater hypophysitis. Withhold KEYTRUDA for moderate (Grade 2) hypophysitis, withhold or discontinue KEYTRUDA for severe (Grade 3) hypophysitis, and permanently discontinue KEYTRUDA for lifethreatening (Grade 4) hypophysitis.

Renal Failure and Immune-Mediated Nephritis

Nephritis occurred in 3 (0.7%) patients, consisting of one case of Grade 2 autoimmune nephritis (0.2%) and two cases of interstitial nephritis with renal failure (0.5%), one Grade 3 and one Grade 4. The time to onset of autoimmune nephritis was 11.6 months after the first dose of KEYTRUDA (5 months after the last dose) and lasted 3.2 months; this patient did not have a biopsy. Acute interstitial nephritis was confirmed by renal biopsy in two patients with Grades 3-4 renal failure. All three patients fully recovered renal function with treatment with high-dose corticosteroids (greater than or equal to 40 mg prednisone or equivalent per day) followed by a corticosteroid taper.

Monitor patients for changes in renal function. Administer corticosteroids for Grade 2 or greater nephritis. Withhold KEYTRUDA for moderate (Grade 2) nephritis, and permanently discontinue KEYTRUDA for severe (Grade 3), or life-threatening (Grade 4) nephritis.

Immune-Mediated Hyperthyroidism and Hypothyroidism

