Other clinically important immune-mediated adverse reactions can occur. The following clinically significant, immune-mediated adverse reactions occurred in less than 1% of patients treated with KEYTRUDA in Trial 1: exfoliative dermatitis, uveitis, arthritis, myositis, pancreatitis, hemolytic anemia, partial seizures arising in a patient with inflammatory foci in brain parenchyma, Guillain-Barré syndrome, vitiligo, encephalitis, and adrenal insufficiency. Across clinical studies with KEYTRUDA in approximately 2000 patients, the following additional clinically significant, immune-mediated adverse reactions were reported in less than 1% of patients: myasthenic syndrome, optic neuritis, rhabdomyolysis and sarcoidosis in parts of the lymph nodes, skin, or lungs.

For suspected immune-mediated adverse reactions, ensure adequate evaluation to confirm etiology or exclude other causes. Based on the severity of the adverse reaction, withhold KEYTRUDA and administer corticosteroids. Upon improvement to Grade 1 or less, initiate corticosteroid taper and continue to taper over at least 1 month. Based on limited data from clinical studies in subjects whose immune-related adverse reactions could not be controlled with corticosteroid use, administration of other systemic immunosuppressants can be considered. Restart KEYTRUDA if the adverse reaction remains at Grade 1 or less. Permanently

discontinue KEYTRUDA for any severe or Grade 3 immune-mediated adverse reaction that recurs and for any life-threatening immune-mediated adverse reaction.

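### Section 9.1.4 holds or stops pembrolizumab on PT/INR grade, but these documents never order PT/INR during treatment; separately, Grade 3 bilirubin has two different actions

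*Combined protocol and SAP*

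**What the plan says.** The Immune-Mediated Hepatitis part of Section 9.1.4 uses coagulation results in three rules:

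- Treatment is interrupted when transaminase or alkaline phosphatase "increases are accompanied by Grade 3 total bilirubin, and/or Grade 3 coagulation tests (e.g., International Normalized Ratio [INR"), or when the patient has symptoms.
- For Grade 2-3 "total bilirubin or PT/INR, pembrolizumab should be interrupted and steroids given as above". If values do not improve "within 12 weeks from date of diagnosis of grade 3 toxicity to baseline or Grade 0-1", the drug is stopped for good.
- For Grade 4 "total bilirubin or PT/INR, pembrolizumab should be permanently discontinued".

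On what to do when liver tests rise, the same section says: "Evaluation of subjects with elevated transaminases, bilirubins, and alkaline phosphatase should involve a workup to assess for infection (SBP or other"), followed by further causes to consider. For Grade 3-4 enzyme events it adds a condition on cause: "and no other underlying etiology is found, consider treatment with intravenous corticosteroids". The Grade 2-3 bilirubin and PT/INR bullet carries no such condition.

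PT/INR is scheduled in Section 12.1 (screening) and Section 12.4 (30 days after Off Treatment). Table 10.2 has a row for increased bilirubin (withhold at Grade 2, permanently discontinue at Grade 3 or 4) and no row for PT/INR.

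**The concern.** A hold or stop rule works only if someone measures the quantity that it acts on. A site that follows these documents to the letter could give the next dose to a patient with worsening liver tests who already meets a PT/INR criterion, because nothing in them says to draw the test. The population makes this relevant. Child-Pugh scores up to 7 are eligible, INR is one of the Child-Pugh components (Appendix G), and PT of at most 16 seconds is an entry criterion, so the plan treats coagulation as informative at entry.

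The bilirubin conflict is a separate matter. Two clinicians with the same patient at Grade 3 bilirubin could each follow the protocol; one would hold the drug and the other would end it permanently.

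**Working it through.** No design figure is involved, so the check sets the texts side by side.

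**Step 1. Where PT/INR is scheduled**

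| Place | PT/INR |
|---|---|
| 12.1 Screening | Listed under coagulation studies, apart from liver function tests |
| 12.2.1 Day 1, all cycles | Not listed |
| 12.3 Off-Treatment | Not listed |
| 12.4 30 days after Off Treatment | Listed under coagulation studies, apart from liver function tests |
| 12.6 calendar | Marked for Screening and the 30-day Safety Evaluation only |
| 12.6 footnote E (chemistry panel) | Not included |

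There are two scheduled time points per patient and none during treatment. Liver function tests cannot be read to include PT/INR, because 12.1 and 12.4 list the two separately.

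**Step 2. Whether a liver event triggers it**

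The 9.1.4 workup lists causes to assess. The Grade 2 enzyme rule in 9.1.4 asks for weekly liver function tests. Table 10.2 and Appendix I also call for liver function tests. Section 10.2.1 calls for viral loads and a search for causes. None of them names PT/INR.

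**Step 3. Who is left exposed**

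Other rules already stop dosing in many of these patients. Table 10.2 withholds for Grade 3 AST/ALT and for Grade 2 bilirubin, and 9.1.4 interrupts when raised enzymes come with symptoms. What remains is a patient with worsened liver tests, AST/ALT below Grade 3, bilirubin below Grade 2, no symptoms, and a PT/INR at an action grade. The documents give no rate for this combination.

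**Step 4. The recovery limit**

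12 weeks × 7 = 84 days, and 84 / 21 = 4 cycle lengths. No PT/INR is scheduled in that time while treatment visits continue.

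**Step 5. Section 9.1.4 against Section 10**

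| Finding | 9.1.4 | 10.1 and Table 10.2 |
|---|---|---|
| Bilirubin Grade 2 | Interrupt, steroids | Withhold, steroids |
| Bilirubin Grade 3 | Interrupt, up to 12 weeks to recover | Permanently discontinue |
| Bilirubin Grade 4 | Permanently discontinue | Permanently discontinue |
| PT/INR Grade 2 | Interrupt, steroids | No row; catch-all withholds only if intolerable or persistent |
| PT/INR Grade 3 | Interrupt, up to 12 weeks to recover | No row; catch-all withholds or discontinues by type of event |
| PT/INR Grade 4 | Permanently discontinue | No row; catch-all and 10.1 discontinue |

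The clear mismatches are Grade 3 bilirubin and Grade 2 PT/INR. Both texts concern immune-related events, so they do apply to the same patient.

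**The case against.** The strongest reply is that testing driven by events is how this protocol works. Table 10.2 acts on myocarditis, yet the ECG is scheduled only at screening. It acts on Grade 3-4 hyperglycemia, yet glucose is not named in the chemistry list. A rule that speaks of enzyme rises accompanied by abnormal coagulation presupposes that an INR is drawn. Section 9.1.4 also says "If an irAE is suspected, a thorough evaluation should be conducted" and, later, "For suspected immune-mediated adverse reactions, ensure adequate evaluation to confirm etiology or exclude other causes". Appendix I foresees unscheduled laboratory testing, and a clinician may order an INR at any time. This stands as an argument against testing at every cycle. It does not supply the missing order. Where the plan wants a conditional test it writes one, as 12.2.1 does for lipase and amylase, and PT/INR has no such line.

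Some stronger readings are tempting, and the documents do not support them:

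- **That no instruction to draw INR exists anywhere.** Section 9.1.4 refers to a separate guidance document on events of clinical interest, and Appendix I points to site guidance in the trial file binder for its hepatic criteria. Neither is available here. The finding is limited to these documents.
- **That every dosing decision is unprotected.** With 35 doses and no delays, 35 − 1 = 34 decisions follow dose 1, over 34 × 21 = 714 days. That count matters only if PT/INR is a stand-alone trigger. The bullets sit in the hepatitis subsection and may only grade an event already found on liver tests; the text does not settle which.
- **That the 12-week limit cannot be applied.** For PT/INR the clock presupposes a measured Grade 3 value, and a clinician who held the drug on that value would have to repeat it. The text merely fails to say so.
- **That Table 10.2 plainly overrides 9.1.4.** Section 10.2 uses mandatory wording and 9.1.4 advisory wording, which favors the table, but no sentence says that it prevails.

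**Conclusion.** The point holds in limited form and should be fixed. In these documents a stated hold or stop rule lacks its input during treatment. The exposed group is narrow, because AST/ALT, bilirubin and a physical examination are done every cycle and carry holds of their own. How many patients would be affected, or how many events missed, cannot be derived. DCR and the error rates of the two-stage design are not touched.

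The Grade 3 bilirubin conflict is explicit and does not depend on the PT/INR schedule, since bilirubin is measured every cycle.

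The conclusion assumes that a site works from the protocol text. If the separate site guidance already orders PT/INR with liver events, the first part becomes a matter of bringing that instruction into the protocol. The bilirubin conflict would remain.

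**What to change.** 1. In 9.1.4, 12.2.1 and 12.6, require PT/INR with the liver-test draw when AST/ALT or alkaline phosphatase reaches the event thresholds of 9.1.4 (Grade 2 or higher if normal or Grade 1 at baseline, or more than 3 times baseline if above 2 times ULN at baseline), or when bilirubin is Grade 2 or higher. Otherwise draw it if clinically indicated. Repeat an abnormal value until recovery, so that the 12-week limit can be applied. A grade threshold is needed because patients may enter with AST/ALT up to 5 times ULN, and a trigger on any rise would fire on small fluctuations.
2. Make the Grade 2-3 PT/INR rule apply only when no other cause is found, as the enzyme bullets already do. Otherwise INR rises that are not immune-related, in patients with cirrhosis or progressing tumor, would force holds and steroids.
3. Align 9.1.4 with Table 10.2 by permanently discontinuing for Grade 3 or 4 bilirubin, including in the sentence on enzyme rises with Grade 3 bilirubin. Add a PT/INR row to the table that matches 9.1.4 as amended.

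The cost is one coagulation tube at liver-test draws that meet the threshold, and one amendment. Item 3 also removes the 12-week recovery period for Grade 3 bilirubin that 9.1.4 now allows. PT/INR at every cycle is not needed.

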8.4 Supportive Care Guidelines

Subjects should receive appropriate supportive care measures as deemed necessary by the treating Investigator. Suggested supportive care measures for the management of adverse events (AEs) with potential immunologic etiology are outlined below. Where

appropriate, these guidelines include the use of oral or intravenous treatment with corticosteroids as well as additional anti-inflammatory agents if symptoms do not improve with administration of corticosteroids.

Note that several courses of steroid tapering may be necessary as symptoms may worsen when the steroid dose is decreased. For each disorder, attempts should be made to rule out other causes such as metastatic disease or bacterial or viral infection, which might require additional supportive care.

It may also become necessary to perform conditional procedures such as bronchoscopy, endoscopy, or skin photography as part of evaluation of the event. Suggested conditional procedures for Events of Clinical Interest (ECI) associated with pembrolizumab, can be found in Appendix I.

The treatment guidelines are intended to be applied when the Investigator(s) determine the events to be related (possible, probable or definite) to trial treatment. Note: if after an evaluation the event is determined not to be related to the trial treatment, the Investigator is instructed to follow the reporting guidance in Appendix A (and Section 15.0). Refer to Section 10.0 for dose modification(s).

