10.0 TREATMENT/ DOSE MODIFICATIONS

10.1 Unacceptable Toxicity

Causality for all adverse events should be assessed and if deemed attributable, attempts should be made toward proper attribution.

Drug-related grade 4 toxicities will require subject to discontinue all study treatment. Intolerable grade 2 and grade 3 toxicities should be managed as per dose modification guidelines listed in the table below. Pembrolizumab therapy may be continued providing the residual adverse events are within permissible ranges for pembrolizumab dosing.

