10.2 Dose Modification Guidelines for Pembrolizumab

Adverse events (AEs) both serious and non-serious associated with pembrolizumab exposure may represent an immunologic etiology. These AEs may occur shortly after the first dose or several months after the last dose of treatment. Pembrolizumab must be withheld for drug-related toxicities and severe or life-threatening AEs as per Table 10 below. See also Section 8.4 for supportive care guidelines and Appendix I.

Dosing interruptions are permitted in the case of medical/surgical events or logistical reasons not related to study therapy (e.g. elective surgery, unrelated medical events, patient vacation, and/or holidays). Subjects should be placed back on study therapy within 3 weeks of the scheduled interruption, unless otherwise discussed with the PI. The reason for the interruption should be documented in the patient's study record.

Table 10.2 Dose Modification and Toxicity Management Guidelines for Immune-related AEs Associated with Pembrolizumab

General instructions:				

 1. Corticosteroid taper should be initiated upon AE improving to Grade 1 or less and continue to taper over at least 4 weeks. 2. For situations where pembrolizumab has been withheld, pembrolizumab can be resumed after AE has been reduced to Grade 1 or 0 and corticosteroid has been tapered. Pembrolizumab should be permanently discontinued if AE does not resolve within 12 weeks of last dose or corticosteroids cannot be reduced to ≤ 10 mg prednisone or equivalent per day within 12 weeks. 3. For severe and life-threatening irAEs, IV corticosteroid should be initiated first followed by oral steroid. Other immunosuppressive treatment should be initiated if irAEs cannot be controlled by corticosteroids. 				
Immune-related AEs	Toxicity grade or conditions (CTCAEv4.0)	Action taken to pembrolizumab	irAE management with corticosteroid and/or other therapies	Monitor and follow-up
Steven-Johnson Syndrome (SJS)	Any	Permanently discontinue	Refer patient for specialized care for assessment and treatment.	If SJS confirmed, permanently discontinue pembrolizumab
Toxic Epidermal Necrolysis (TEN)	Any	Permanently discontinue	Refer patient for specialized care for assessment and treatment.	If TEN confirmed, permanently discontinue pembrolizumab

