Pneumonitis	Grade 2	Withhold	Administer corticosteroids (initial dose of 1-2 mg/kg prednisone or equivalent) followed by taper	Monitor participants for signs and symptoms of pneumonitis Evaluate participants with suspected pneumonitis with radiographic imaging and initiate corticosteroid treatment Add prophylactic antibiotics for opportunistic infections
	Grade 3 or 4, or recurrent Grade 2	Permanently discontinue		
Diarrhea / Colitis	Grade 2 or 3	Withhold	Administer corticosteroids (initial dose of 1-2 mg/kg prednisone or equivalent) followed by taper	
 • Monitor participants for signs and symptoms of enterocolitis (ie, diarrhea, abdominal pain, blood or mucus in stool with or without fever) and of bowel perforation (ie, peritoneal signs and ileus). • Participants with \geq Grade 2 diarrhea suspecting colitis should consider GI consultation and performing endoscopy to rule out colitis. • Participants with diarrhea/colitis should be advised to drink liberal quantities of clear fluids. If sufficient oral fluid intake is not feasible, fluid and electrolytes should be substituted via IV

	Grade 4	Permanently discontinue		infusion.
AST / ALT elevation	3	Withhold	Administer corticosteroids (initial dose of 0.5- 1 mg/kg prednisone or equivalent) followed by taper	Monitor with liver function tests (consider weekly or more frequently until liver enzyme value returned to baseline or is stable
	4	Permanently discontinue --see exception below ²	Administer corticosteroids (initial dose of 1-2 mg/kg prednisone or equivalent) followed by taper	
Increased bilirubin	Grade 2	Withhold	Administer corticosteroids (initial dose of 0.5- 1 mg/kg prednisone or equivalent) followed by taper	Monitor with liver function tests (consider weekly or more frequently until liver enzyme value returned to baseline or is stable
	Grade 3 or 4	Permanently discontinue	Administer corticosteroids (initial dose of 1-2 mg/kg prednisone or equivalent) followed by taper	
Type 1 diabetes mellitus (T1DM) or Hyperglycemia	Newly onset T1DM or Grade 3 or 4 hyperglycemia associated with evidence of β -cell failure	Withhold	Initiate insulin replacement therapy for participants with T1DM Administer anti-hyperglycemic in participants with hyperglycemia	Monitor participants for hyperglycemia or other signs and symptoms of diabetes.

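### The re-dosing rules disagree: Grade 3 bilirubin is a hold in Section 9.1.4 but a permanent stop in Table 10.2, and Grade 4 endocrine events are stops in Section 10.1 but may be held, resumed or treated through under Table 10.2

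*Combined protocol and SAP*

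**What the plan says.** All of the following is current text in the combined protocol and SAP.

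**Bilirubin.** The hepatitis part of Section 9.1.4 states, for Grade 2-3, that for "total bilirubin or PT/INR, pembrolizumab should be interrupted and steroids given as above". If values do not improve "within 12 weeks from date of diagnosis of grade 3 toxicity to baseline or Grade 0-1, pembrolizumab should be permanently discontinued"; Grade 4 is a permanent stop. An earlier paragraph in the same part also speaks of interrupting treatment when enzyme rises come with Grade 3 total bilirubin. In Table 10.2, the row "Increased bilirubin" withholds at Grade 2 and permanently discontinues at Grade 3 or 4.

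**Grade 4 events.** Section 10.1 says "Drug-related grade 4 toxicities will require subject to discontinue all study treatment", and then "Intolerable grade 2 and grade 3 toxicities should be managed as per dose modification guidelines listed in the table below". Section 9.1.4 requires a permanent stop for Grade 4 hypophysitis and for Grade 4 hyperthyroidism. It allows isolated hypothyroidism to be treated with replacement hormone while drug continues. In Table 10.2:

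- Grade 3 or 4 hypophysitis and hyperthyroidism may be withheld or permanently stopped, which footnote 1 leaves to the physician.
- New type 1 diabetes, or Grade 3 or 4 hyperglycemia with beta-cell failure, is withheld.
- Grade 2-4 hypothyroidism continues on drug.
- The closing NOTE lets a withheld Grade 3 or 4 endocrinopathy resume at Grade 2 or less once controlled.

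**Which text governs.** Section 8.4 points to Section 10.0 for dose modification. Section 10.2 says "Pembrolizumab must be withheld for drug-related toxicities and severe or life-threatening AEs as per Table 10 below". Neither says that the table overrides Section 9.1.4 or Section 10.1.

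**The concern.** The rule that is followed decides whether a patient is re-exposed after a Grade 3 bilirubin event or a Grade 4 endocrine event, and whether that re-dose is a protocol deviation. A patient with Grade 3 bilirubin who recovers by week 6 may be re-dosed under Section 9.1.4 but not under Table 10.2. The population makes the bilirubin rule relevant: Section 5.1 admits Child-Pugh scores up to 7 and bilirubin just under 2 mg/dL. The number of doses received and the reasons for discontinuation, which Section 16.5 summarizes, would also depend on which section the investigator applied.

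**Working it through.** The protocol gives no figure of its own to reproduce here. The check is a comparison of the rules, followed by a rough count of the patients affected.

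**Rules side by side**

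| Event | Section 9.1.4 | Section 10.1 | Table 10.2 | Does one action satisfy all? |
|---|---|---|---|---|
| Grade 3 total bilirubin | Interrupt; stop if no recovery in 12 weeks | Refers intolerable Grade 2 and Grade 3 to the table | Permanent stop | Yes: stop |
| Grade 4 hypophysitis | Permanent stop | Stop | Withhold or stop; may resume | Yes: stop |
| Grade 4 hyperthyroidism | Permanent stop | Stop | Withhold or stop; may resume | Yes: stop |
| Grade 4 hyperglycemia or type 1 diabetes | No paragraph of its own | Stop | Withhold; may resume | Yes: stop |
| Grade 4 hypothyroidism | Drug may continue (isolated hypothyroidism) | Stop | Continue | No |

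In the first four rows a permanent stop breaks no instruction, because resumption is never compulsory. The conflict there is that one section permits a re-dose that another forbids. In the last row Section 10.1 and the table give opposite instructions, and Section 9.1.4 agrees with the table.

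Reading the table as governing would settle bilirubin but not the endocrine events, because that conflict also lies inside Section 10. Section 10.1 sends only intolerable Grade 2 and Grade 3 events to the table, while the opening of Section 10.2 sends life-threatening events there too.

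**Patients likely to be affected**

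Inputs: n = 28 evaluable or 35 enrolled (Section 16.4); Grade 4 hypophysitis in 1 of 411 and hepatitis of any grade in 2 of 411 (Section 9.1.4, Trial 1, the source of its 411-patient melanoma figures). For a rate f, the expected number is n × f and the chance of at least one event is 1 − (1 − f)^n.

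- Grade 4 hypophysitis, f = 1/411 = 0.00243. Expected: 28 × 0.00243 = 0.07 and 35 × 0.00243 = 0.09. Chance of at least one: 1 − (1 − 0.00243)^28 = 6.6% and, with exponent 35, 8.2%. The exact 95% interval for f is 0.006% to 1.35%, which gives 0.2% to 32% (n = 28) and 0.2% to 38% (n = 35).
- Hepatitis of any grade, f = 2/411 = 0.00487. Expected: 0.14 and 0.17. Chance of at least one: 12.8% and 15.7%. The exact 95% interval for f is 0.059% to 1.75%, which gives 1.6% to 39% and 2.0% to 46%.

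The second figure is only a proxy. The documents give no rate for Grade 3 bilirubin. In the 41 HCC patients given another PD-1 antibody (Section 1.1), bilirubin is not among the Grade 3-4 events listed as above 5%.

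**The case against.** The best defense is that the intended precedence is fairly clear. Section 9 concerns the agent and its supply, and Section 9.1.4 reads largely as reference safety information. It describes its immune-event advice as general guidance and leaves permanent discontinuation open to discussion between sponsor and investigator. Section 10 is the dose-modification section, and Sections 8.4 and 10.2 both point to it. The endocrine NOTE can be read as a specific exception to the general Grade 4 rule, and Appendix I, which advises insulin for Grade 3-4 hyperglycemia without asking for a permanent stop, fits the table.

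Much of this stands, and it supports making the table govern over Section 9.1.4. It does not remove the point. Section 9.1.4 also carries trial-specific instructions, such as the HBV viral-load entry limit and sponsor consultation within 24 hours. The Grade 4 rule in Section 10.1 has no endocrine exception, and no sentence supplies one.

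A reader might go further and infer that these instructions cannot be followed at all. The documents do not support that: a permanent stop complies everywhere except for Grade 4 hypothyroidism. Nor should the Section 9.1.4 rule on life-threatening reactions be counted as another breach. It sits under the heading for other immune-mediated reactions, while hypophysitis and hyperthyroidism have their own paragraphs, and applying it to hyperglycemia is inference.

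**Conclusion.** The inconsistency is real and in current operative text. For Grade 3 bilirubin and for Grade 4 hypophysitis, hyperthyroidism and hyperglycemia or type 1 diabetes, one section permits a re-dose that another forbids. For Grade 4 hypothyroidism, two instructions in Section 10 contradict each other outright.

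The likely number of patients is small: well under one expected Grade 4 hypophysitis, if melanoma rates carry over to HCC. The interval is too wide to say more, and no Grade 3 bilirubin rate is available. The reason to act is that the rule concerns re-exposure after severe toxicity and is cheap to correct.

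A reader might infer that the trial's decision rules are affected. They are not: the Simon boundaries in Section 16.2 (3 of 14 and 9 of 28) and the toxicity guideline in Section 17.2.2 are defined by response and by toxicity events, not by which dosing rule was applied.

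**What to change.** In the next amendment:

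1. **Section 10.2:** state that Table 10.2 governs holds and permanent stops over Section 9.1.4 and Appendix I. Do not place it over Section 10.1 across the board. The Grade 4 AST/ALT row points to an exception in footnote 2 that deals only with Grade 3, so the Grade 4 stop in Section 10.1 is a needed backstop.
2. **Section 9.1.4, hepatitis bullets, total bilirubin only:** make the interruption apply to Grade 2 instead of Grade 2-3, and the permanent stop to Grade 3 or 4 instead of Grade 4. The present 12-week clock starts at a Grade 3 diagnosis, so tie the remaining Grade 2 hold to general instruction 2 of the table: "Pembrolizumab should be permanently discontinued if AE does not resolve within 12 weeks of last dose". Leave PT/INR unchanged, since the table has no such row.
3. **Section 9.1.4, paragraph on enzyme rises:** refer Grade 3 total bilirubin to Table 10.2, with permanent discontinuation if immune-related.
4. **Section 10.1:** keep the Grade 4 stop and add only an exception for endocrinopathies, which follow Table 10.2.
5. **Grade 4 hypophysitis and hyperthyroidism:** make Section 9.1.4, the table rows and the NOTE agree. Either Section 9.1.4 adopts the table's choice between withholding and stopping, or, if re-dosing is not intended, the rows are split so that Grade 4 is a permanent stop, the NOTE is limited to Grade 3 for these two events, and the Section 10.1 exception covers only hypothyroidism and hyperglycemia or type 1 diabetes.

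The cost is a few sentences, with no new data, visits or patients. The downside is that some patients who recover from Grade 3 bilirubin come off drug. The first option in item 5 keeps re-dosing after a Grade 4 event possible, so the sponsor has to choose deliberately.
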